8.1 STUDY DESIGN

This is a randomized, controlled, parallel observer-blind group study. Subjects providing informed consent will be screened against the inclusion/exclusion criteria. Subjects who meet all of the inclusion criteria and none of the exclusion criteria will be randomly assigned in an equal allocation ratio (1:1) to either SANTYL or to the hydrogel control according to a pre-determined randomization schedule using a blocking technique. Subject randomization will be stratified by the Subject's wound size at baseline resulting in two possible strata: ≥1.0 and ≤10.0 cm²; and >10.0 and ≤64.0 cm². A blocked design will be used for each individual stratum. In either case, caregivers will apply test article once daily (more often as needed for compromised dressing integrity) for up to 6 weeks.

If the ulcer is closed and completely re-epithelialized prior to the end of the 6 week treatment period in either group, the subject will complete Study Visit 7 (Exit) and will be dismissed from the study.

At each weekly visit, the target ulcer will be photographed and area measured using the ImageIQ EDCIQ mobile imaging system. At Study Visit 1 and at Study Visit 7, the ulcer will be assessed using the PUSH and WBS tools. In addition, resource utilization information will be collected at each study visit as described in Section 9.5.

Figure 8.1-1: Study Flow Chart

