10. STATISTICAL DESIGN

A formal Statistical Analysis Plan (SAP) (also referenced to as the Statistical Considerations) will be written and finalized prior to database lock. The SAP will detail the summaries and analyses to be performed.

Smith & Nephew Wound Management Global Medical and Clinical Affairs Department will conduct data management and statistical analysis. Unless otherwise stated, all significance tests and hypothesis testing will be two-sided, performed at the 5% significance level. Resulting p-values will be quoted and 95% two-sided confidence intervals will be generated where appropriate. All analyses will be performed in SAS v9.4 (or later).

Where data summaries are specified, categorical and ordinal variables will be summarized using frequency distributions which will detail the number and percentage of subjects which fall into each category. Continuous variables will be summarized using the following summary statistics: mean, median, standard deviation, minimum and maximum values, and number of observations.

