An initial linear regression model will contain covariates for treatment, baseline (defined as Study Visit 1) ulcer area, baseline percentage of nonviable tissue, and duration of ulcer. A forward selection procedure will be used for the addition of other baseline covariates with an F-value to attain a significance level of 0.1. Further baseline covariates to be assessed as part of this procedure include: subject age, baseline (maximum) ulcer depth, baseline PUSH and WBS scores. The resulting primary analysis presented will correspond to the final model from the forward selection procedure. The results for the initial model will also be presented. For each of the effects in the initial and final model, the p-value, parameter estimate and corresponding 95% confidence interval will be presented. Secondary subgroup analyses may be conducted as a result of the covariate analyses. Additionally, treatment will be fitted on its own in a further linear regression model. The potential for interactions will be examined by fitting the required interaction terms in addition to those effects in the final linear regression model from the forward selection procedure. In each case if the residuals are not normally distributed then non-parametric bootstrapping will be applied. If the nonparametric bootstrap estimates of the confidence intervals for the difference in mean percentage reduction in area between treatments

differ considerably to the standard model estimates, then the nonparametric bootstrap estimates will be used.

The percentage reduction in wound area over the 6-week treatment period will be summarized by treatment separately by the covariates used in the final model.

In addition, a two-sample t-test will be used to test for a difference between treatments in the mean percentage reduction in wound area between Visit 1 and Visit 2. The test will be repeated for comparisons between Visit 1 and Visits 3, 4, 5 and 6 individually. In each case, if normality assumptions do not hold, a Wilcoxon Rank Sum test will be used.

The wound area, reduction in wound area and percentage reduction in wound area at each study visit will be summarized by treatment separately by baseline wound area strata and overall.

The reduction in percentage non-viable necrotic tissue over the 6-week treatment period and at each assessment visit

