- 2) The "best case" value will be used. That is, the lowest value of percentage non-viable necrotic tissue recorded by the two independent reviewers at each time point will be used for purposes of analysis.

Change in Wound Status as measured by the PUSH and WBS tools following 6 weeks of treatment

Wound status will be measured by both the PUSH and WBS tools at Study Visit 1 and at Study Visit 7 (Exit).

At both Study Visit 1 and Study Exit, the PUSH Tool (version 3.0) will be scored according to the instructions for use (18.1.1). The sub-scores for Length/Width, Exudate Amount, and Tissue Type will be recorded. The Total Score, on a scale of 0-17, will then be derived by taking the sum of the three sub-scores detailed previously.

The reduction in PUSH individual sub-scores will be derived as follows; the reduction in Total Score will be derived using the same method:

PUSH Score at Visit 1 - PUSH Score at Exit Visit

A Wilcoxon Rank Sum test will be used to test for a difference between treatments in the reduction in Total PUSH Score over the 6-week treatment period.

The responses to the individual sub categories (Length/Width, Exudate Amount, and Tissue Type) will be summarized by treatment at each visit; in addition the reduction over the 6-week treatment period in each sub-score and total score will be summarized by treatment.

The WBS will be scored at the Study Visit 1 and Study Exit according to the instructions for use (18.1.2). The individual wound bed score characteristics, on a scale of 0-2, will be summed to derive the Total WBS on a scale of 0-16.

The reduction in Total WBS will be derived as follows:

Total WBS Score at Visit 1 - Total WBS Score at Exit Visit

A Wilcoxon Rank Sum test will be used to test for a difference between treatments in the reduction in Total WBS over the 6-week treatment period.

The responses to the individual wound bed score characteristics (Healing edges, Black eschar, etc.) will be summarized by treatment at each visit.

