11. SAMPLE SIZE JUSTIFICATION

A previous study (7) with a design essentially identical to the present study demonstrated highly significant differences between treatment groups for achievement of complete debridement (85% vs. 29%, P<0.003), reduction in % area of non-viable tissue for each week (P<0.002), and in reduction in wound area (P<0.009). The sample size of this previous trial was 27 subjects, 13 in the SANTYL group, and 14 in the hydrogel group. Based on the reported outcomes in the previous trial, 26 subjects are required to detect a difference in the primary endpoint: the proportion of ulcers achieving complete debridement during the 6-week treatment period. This relates to a Fisher's Exact test assuming 85% vs 29% in the proportion of ulcers achieving complete debridement. To allow for 15% drop-out rate throughout the 6-week treatment period, a total of 32 subjects will be randomized (16 per treatment) in an equal allocation ratio for SANTYL and hydrogel. In the previous studies quoted, the secondary endpoints including reduction in % area of non-viable tissue and reduction in wound area were found to reach significance with similar numbers.

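### Total PUSH and Total WBS reductions are tested with neither baseline score nor size stratum in the model; pre-specifying ANCOVA would cost little and could gain precision, by an amount the documents do not fix

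*Combined protocol and SAP*

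**What the plan says.** Section 10.3.2 defines the PUSH and WBS reductions as the Visit 1 total minus the Exit total. For PUSH, "A Wilcoxon Rank Sum test will be used to test for a difference between treatments in the reduction in Total PUSH Score"; the WBS test has the same form. Neither has a covariate or a stratum term.

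For wound area at Visits 2 to 6, "a two-sample t-test will be used to test for a difference between treatments" in mean percentage reduction, with a Wilcoxon test if normality fails. The same comparison is repeated for the reduction in percentage non-viable tissue. These tests are also unadjusted.

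Section 8.1 stratifies randomization by baseline size (1.0 to 10.0 cm², and above 10.0 up to 64.0 cm²) and adds that "A blocked design will be used for each individual stratum". For the endpoints at issue, the strata reappear only in descriptive summaries of area by visit.

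The 6-week models for area and non-viable tissue in section 10.3.2 do adjust, for baseline area, baseline percentage non-viable tissue and ulcer duration. Baseline PUSH and WBS are offered to forward selection there and in the debridement models, but not in the PUSH and WBS analyses themselves. Section 10 leaves further detail to a SAP to be finalized before database lock.

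**The concern.** Subtracting baseline removes the influence of baseline on the exit score only if the regression slope of exit on baseline is 1. There is reason to doubt that for PUSH. Size supplies 10 of its 17 points, in unequal bands with a ceiling (Appendix 18.1.1): every length-by-width product above 24 cm² scores 10. A product that falls 60%, from 64 to 25.6 cm², shows no change in the size sub-score. The same 60% fall from 4.0 to 1.6 cm² moves it from 6 to 4. So the reduction can depend on starting size, which is also the stratification factor.

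At stake is the precision of two secondary comparisons in a trial of about 26 to 32 subjects. A secondary question is consistency: area and non-viable tissue are baseline-adjusted at 6 weeks but not at Visits 2 to 6, and no reason is given.

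**Working it through.** **1. The plan's own figure.** Section 11 says "26 subjects are required to detect a difference in the primary endpoint" and "This relates to a Fisher's Exact test assuming 85% vs 29% in the proportion of ulcers achieving complete debridement". Section 10 sets two-sided tests at 5%, and section 8.1 sets 1:1 allocation. Exact enumeration of Fisher's test gives power of 74.2% at 12 per arm and 80.9% at 13 per arm. So 26 is the smallest equal-arm total that reaches 80% (a target I assume, as none is stated). With 15% dropout, 13/0.85 = 15.3, rounded up to 16 per arm, or 32. Both figures reproduce. The documents give no power or precision figure for PUSH, WBS or the visit-by-visit tests.

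**2. Variance of the adjusted estimate relative to the change score.** Let r be the baseline-exit correlation and k the exit SD divided by the baseline SD. Neither is in the documents, so I show a range. In units of the baseline variance, the change score has variance 1 + k² − 2rk and the baseline-adjusted residual has variance k²(1 − r²). The large-sample ratio is

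k²(1 − r²) / (1 + k² − 2rk), which becomes (1 − r²)/(2(1 − r)) = (1 + r)/2 when k = 1.

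| k | r = 0.3 | r = 0.5 | r = 0.7 |
|---|---|---|---|
| 1 | 0.65 | 0.75 | 0.85 |
| 1.5 | 0.87 | 0.96 | 1.00 |
| 2 | 0.96 | 1.00 | 0.93 |

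The ratio cannot exceed 1, because the change score is the adjusted estimate with its slope fixed at 1.

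**3. Small-sample cost.** Estimating the covariate slopes inflates the variance by about 1 + 1/(N − 4) for one covariate and 1 + 2/(N − 5) for two. At N = 26 these are 1.045 and 1.095; at N = 32, 1.036 and 1.074. At k = 1, r = 0.5 and N = 32 the net ratio is 0.75 × 1.074 = 0.81. Where the ratio in step 2 is already about 1.00, adjustment gains nothing and costs a few percent.

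**4. Simulated power.** Scores were PUSH-like integers with two size strata, allocation balanced within stratum and an effect of one exit SD. Fourteen per arm is roughly 16 × 0.85 = 13.6. Entries are Wilcoxon on the change against ANCOVA with baseline and stratum.

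| Per arm | k | r = 0.3 | r = 0.5 | r = 0.7 |
|---|---|---|---|---|
| 14 | 1 | 54% vs 73% | 70% vs 81% | 89% vs 93% |
| 16 | 1 | 59% vs 78% | 75% vs 87% | 92% vs 96% |
| 16 | 1.5 | 72% vs 78% | 85% vs 87% | 95% vs 95% |

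These contrasts combine the effects of baseline adjustment, the stratum term and the move from ranks to means. At 13 and 16 per arm, stratifying the Wilcoxon alone (van Elteren) changed power by about −2 to +7 points, so most of the gain does not come from the stratum alone.

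**5. Type I error.** At 13 and 16 per arm, the rejection rate of the planned Wilcoxon under the null was 2.5% to 5.8%, mostly below 5%. At 14 per arm with k = 1 it was about 3%, while ANCOVA was near 5%.

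**6. Visits 2 to 6.** Percentage area reduction is not a simple difference, so the ratio in step 2 does not apply and I give no figure. For non-viable tissue, section 7.2 restricts baseline to 85% or more. If baseline is uniform on 85 to 100, its SD is 15/√12 = 4.3. With later SDs of 20 to 40 and r from 0 to 0.3 (assumed), the ratio is 0.96 to 1.00.

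**The case against.** The planned tests are defensible. PUSH (0 to 17) and WBS (0 to 16) are bounded ordinal sums in a small trial, and a rank test avoids assuming linearity or normality. Section 4.2 aims to replicate an earlier study closely, although its list of replicated features does not include the statistical tests.

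The documents also give reason to expect k above 1, where the gain is small. Entry requires at least 85% necrotic tissue, so the PUSH tissue sub-score starts at or near its top and can fall to 0 by exit. Rank ANCOVA is not a reliable remedy: at 16 per arm and k = 1.5 its power was 76%, 85% and 93%, against 72%, 85% and 95% for the planned Wilcoxon. All of this stands, and it limits the claim to a probable improvement of uncertain size.

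A reader might infer that the plan discards the baseline value. It does not: baseline is subtracted for PUSH, WBS and non-viable tissue, and is the denominator for percentage area reduction. What is missing is baseline as a covariate. A reader might also infer that leaving out the strata invalidates the tests. Step 5 shows the reverse, and blocking by size already limits imbalance on that factor.

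**Conclusion.** The point holds for PUSH and WBS as a matter of efficiency. Baseline-adjusted ANCOVA is at least as precise as the change score, apart from the small cost in step 3. Over r from 0.3 to 0.7, the large-sample saving is 15% to 35% of the variance if the two SDs are equal, and at most 13% if the exit SD is 1.5 to 2 times larger. It is nil in parts of that range. The result rests on assumed r, k and effect size.

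It would be tempting to say that precision is certainly being thrown away. The documents do not support that, because they give neither r nor k. For area at Visits 2 to 6 the case is consistency with the 6-week model; for non-viable tissue the expected gain is close to nil. The planned tests are valid, if somewhat conservative. Only secondary endpoints are touched: the primary analysis and the sample size stand.

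**What to change.** Before database lock, pre-specify in the SAP an ANCOVA of exit Total PUSH, and separately of exit Total WBS, with treatment, the matching baseline score and size stratum. If residuals are non-normal, report non-parametric bootstrap intervals, as section 10.3.2 already provides for area. Keep the planned Wilcoxon tests as supportive analyses.

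For Visits 2 to 6, adjust the area comparisons for baseline area or size stratum, to match the 6-week model. The same may be done for non-viable tissue for uniformity, with little gain to expect.

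The cost is SAP wording, a few lines of code, one or two degrees of freedom, and a linearity assumption on bounded scores. No new data are needed.

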10.3.3 Exploratory Analysis

The exploratory analysis for this study will be a comparison of resource utilization for each treatment group. Resource utilization in the form of nursing time spent on dressing changes, test article utilization, and wound care supplies utilized will be aggregated with descriptive statistics reported by treatment group.

10.4 SAFETY

Safety variables include adverse events (AE), AE will be coded using the Medical Dictionary for Regulatory Activities (MedDRA). The treatment-emergent AEs will be reported separately for the 6-week treatment period (Study Visits 2 to 7) and initial screening period (interval between Screening Visit 1 and Screening Visit 2). Frequency of treatment-emergent AE will be calculated for each body system, by preferred term, by subject group (i.e., SANTYL, hydrogel), for number of subjects and proportion reporting the event for the safety population. The severity of the AE and the relationship to study medication will be summarized for each body system and preferred term by subject group. Withdrawals in general and withdrawals due to AE will be summarized for each body system and preferred term by subject group.

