This visit should occur no more than 7 days after the Screening Visit. Any subject who returns but does not qualify at this visit will be a screen failure and will not be randomized. Upon completion of all screening procedures and confirmation that the subject is eligible for the study, the Investigator or designee will randomize the subject using an electronic randomization system (www.sealedenvelope.com) to obtain the treatment assignment.

The day of the week (Monday, Tuesday, etc.) on which this visit occurs will set the weekly visit day for all subsequent assessments/visits (Study Visits 2 through 7) if the subject is randomized. A (± 1) day visit window will be allowed. If an assessment is not made on the original day of the week for Study Visits 2-7, subsequent visits should be scheduled on the original week day. To minimize differences in baseline ulcer size between the two groups, randomized subjects will be stratified by ulcer size determined at this visit [≥ 1.0 and ≤ 10.0 cm²; ≥ 10.0 and ≤ 64.0 cm²]. Once randomized, subjects will be assessed weekly for the duration of the treatment period (SV1 through SV7).

The following procedures will be completed:

- 1. Record any changes in general health and the use of concomitant medications.
- 2. If any adverse events are observed or reported, they must be recorded as instructed in Section 12, *Adverse Events*.
- Review laboratory results from the blood sample and all other inclusion/exclusion
 criteria.
 - If the blood test results qualify and all entry criteria are met, the subject may be randomized.
- Irrigate the wound with normal saline delivered at 4-15 psi using the Irrimax® device.
 (Sharp debridement is NOT allowed.)
- 5. Photograph the target ulcer using the ImageIQ EDCIQ mobile imaging system. The target ulcer area (cm²) and percentage of the target ulcer surface covered with necrotic, nonviable tissue will be determined by two independent reviewers using the ImageIQ EDCIQ mobile imaging system. The target ulcer area and percentage of necrotic, nonviable tissue must be assessed by at least one independent reviewer prior to the subject being randomized.

Note: If the area of the target ulcer is >64.0 cm², the subject must be screen failed and should not be randomized.

- 6. Assess the wound status using both the PUSH and WBS tools.

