- 7. Apply the test article to the entire wound bed according to the instructions for use located in the Study Guide, cover with a semi-occlusive dressing (e.g. COVRSITETM). If the wound has depth, saline-moistened gauze may be used to fill at the Investigator's discretion.
- Ensure that all caregivers are instructed as to the treatment requirements for the study
 protocol and that they are instructed in the application of test article and dressing changes.

Ensure adequate supplies (test article and dressings) are dispensed.

- 9. Record the time spent dressing the ulcer at this visit.
- 10. Schedule the assessment, Study Visit 2, in 7 (± 1) days.

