Further details, including model assumptions and diagnostics to be examined are included in the study SAP. The preceding analysis will be repeated using the Per Protocol Population.

Kaplan-Meier plots will be presented by treatment, baseline wound area strata, baseline percentage of nonviable tissue and ulcer duration (categorized) and also to represent all covariates with significant effects in the final survival analysis model. Individual plots for multiple factors will be generated where appropriate.

In addition, a sensitivity analysis will be performed to ensure that the efficacy findings are not reliant on assumptions made in either the analysis or derivations. For purposes of the sensitivity analysis, the time to confirmed complete debridement for those subjects discontinuing the treatment period prematurely will be censored at the maximum possible duration of treatment under the study protocol (42 days), rather than time of actual discontinuation. Lastly, the two sensitivity analyses defined in the proportion of subjects achieving complete debridement analysis will be repeated for the time to achieve complete debridement; in these cases the

censoring flag may be modified as detailed previously in the primary analysis, but the time in days will remain unchanged.

The percentage reduction in wound area over the 6-week treatment period and at each assessment visit

Wound area is defined as surface area as measured by the ImageIQ EDCIQ mobile imaging system at each assessment visit by two independent image reviewers. The percentage change in wound area over the 6-week treatment period is then defined as:

Percentage reduction in wound area over 6-week treatment period= $\left(\frac{Area_{SV1} - Area_{SV1}}{Area_{SV1}}\right) \times 100\right)$

In cases where the wound is closed in the opinion of the Investigator, the wound area will be imputed as 0 cm², resulting in a percentage reduction in wound area of 100%. In circumstances where the wound area is missing at the Study Visit 7 for subjects that have not withdrawn prematurely due to closure, the last observation carried forward (LOCF) method will be used.

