17. STUDY PLAN

Table 17-1: Study Procedures by Visit

	Screening Period	Treatmen Weekly Visi	Exit		
Procedures	Screening Visit	Study Visit 1a	Visits 2-6	Study Visit 7	
Informed Consent	х				
Demographics/Medical History	Х				
Inclusion/Exclusion	х	х			
Irrigation of ulcer		х	X	Xb	
Photography and Measure Ulcer Size	X	X	х	Xe	
Ankle brachial index ^d	Х		- 41		
Blood collection (pre- albumin, HbA1c) ^e	х				
Urine Pregnancy Test ^t	х			х	
PUSH assessment		X		x	
WBS assessment		х		x	
Application of Study Treatment		Х	Х		
Determine/record nursing time at this visit		x	х	х	
Record Adverse Events	х	Assessed throughout the study			
Concomitant Medications	X	Assessed Throughout the study			

a Study Visit 1 should occur within 7 days of the Screening Visit.

b Not applicable if ulcer is closed.

c Photograph ulcer area even if ulcer is closed.

d Only if ulcer is on a lower extremity.

e HbA1c and pre-albumin are required unless a test has been carried out and recorded in chart within 30 days of SCR1

f Must be conducted on all women of child-bearing potential, including those who have had a bilateral tubal ligation.

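### Section 10.4 bounds the adverse event treatment period by Study Visits 2 to 7, although treatment starts at Study Visit 1, and does not say how week-1 events are assigned

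*Combined protocol and SAP*

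**What the plan says.** Section 10.4 sets two reporting periods for adverse events in one sentence. The first is given as "The treatment-emergent AEs will be reported separately for the 6-week treatment period (Study Visits 2 to 7". The second is the "initial screening period (interval between Screening Visit 1 and Screening Visit 2". The sentence calls the events in both periods treatment-emergent. It does not say whether an event belongs to a period by its onset date or by the visit at which it is recorded.

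Other sections describe the same calendar differently:

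- Section 9.1.2 (Randomization/Study Visit 1) says: "Once randomized, subjects will be assessed weekly for the duration of the treatment period (SV1 through SV7".
- Step 7 of the Study Visit 1 procedures is the first treatment: "Apply the test article to the entire wound bed according to the instructions for use". Table 17-1 also shows study treatment applied at Study Visit 1.
- Step 10 of that visit reads: "Schedule the assessment, Study Visit 2, in 7 (± 1) days".
- Section 10.3.2 refers to the "maximum possible duration of treatment under the study protocol (42 days".
- Section 9.1 and Table 17-1 contain one Screening Visit, followed by Study Visit 1 no more than 7 days later. Neither contains a Screening Visit 2.
- Table 17-1 has adverse events recorded at screening and from then on "Assessed throughout the study".

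**The concern.** A treatment-emergent definition needs a start point tied to first exposure. Section 10.4 names a start one visit after first exposure, and it closes the preceding period at a visit that does not exist. The week between the first application and Study Visit 2 therefore has no certain place in the safety tables. That week holds the first contact with each topical product, when an application-site reaction could first appear.

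The safety population (Section 10.1) includes everyone treated at least once, so week-1 exposure is in the denominator wherever its events are counted. With 16 subjects planned per arm (Section 11), moving one subject's event into or out of the treatment period changes that arm's proportion by 1/16 = 6.25 percentage points.

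**Working it through.** **Inputs.** Study Visit 1 is day 0, the day of first application (Section 9.1.2, step 7). Visits are weekly with a ±1 day window around the original weekday (Section 9.1.2). Maximum treatment duration is 42 days (Section 10.3.2).

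**Calendar.** Study Visit k falls on day 7 × (k − 1), so Visit 2 is day 7 and Visit 7 is day 42.

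**Can the plan's own figure of 6 weeks be reproduced?**

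- Interval from Study Visit 1 to Study Visit 7: 42 − 0 = 42 days = 6 weeks (41 to 43 with the window). It reproduces, and it matches Section 9.1.2 and the 42-day maximum.
- Interval from Study Visit 2 to Study Visit 7: 42 − 7 = 35 days = 5 weeks (33 to 37 with both windows). It does not reproduce.
- Six recording visits (2 to 7), each looking back over the week since the visit before: 6 × 7 = 42 days = 6 weeks. It reproduces.

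The 6-week label and the visit numbers in Section 10.4 therefore agree only if the numbers name the visits at which events are recorded. The other half of the sentence, however, is worded as an interval between two visits.

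**Where does an event with onset between first application and Study Visit 2 go?**

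1. *Assigned by onset date, with Screening Visit 2 read as Study Visit 1.* The event is after the screening period and before the treatment period, so it is in neither. The uncovered time is 7 of 42 days: 7/42 = 16.7% (6/42 = 14.3% to 8/42 = 19.0% with the window).
2. *Assigned by onset date, with Screening Visit 2 read as Study Visit 2.* The event is tabulated as screening, although the subject is on treatment.
3. *Assigned by recording visit.* The event is recorded at Study Visit 2 and counted as on treatment, so no week is lost. The error then runs the other way: an event that began before first application but was first recorded at Study Visit 2 is also counted as on treatment.

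**After anchoring on first application.** The treatment period is day 0 to day 42 = 6 weeks. It agrees with Sections 9.1.2 and 10.3.2 and leaves no gap after the pre-treatment period.

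**The case against.** The best defence is the recording-visit reading. At Study Visit 1, adverse events are recorded at step 2 and the test article is applied at step 7, so events recorded in that order are pre-treatment. Study Visit 2 is then the first scheduled visit that can record an on-treatment event, and Visits 2 to 7 look back over exactly six weeks. Section 9.1.3 fits this reading, since it describes Visits 2 to 6 as weekly assessments within the treatment period. Early leavers do not open a gap either, because Section 9.2 requires the Exit Visit (Study Visit 7) for all discontinued subjects. This stands, and it means that a lost week is not certain.

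A reader might infer that one sixth of on-treatment adverse events will be missed, or more if reactions cluster early. The documents do not support that. The one-sixth is a share of planned exposure under the first reading only. It becomes a share of events only if the event rate is also constant over time, and the documents give no onset distribution from which a larger figure could be derived. Nor are events lost from the record: collection is continuous, and serious and test-article-related events go to the sponsor within 24 hours (Section 12.4).

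Two further points stand. The safety summaries are descriptive, with no between-arm test specified, and the same window applies to both arms. Section 10 also leaves the detail of summaries to a SAP to be finalized before database lock. That SAP is not in the text reviewed and could hold an assignment rule.

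The defence does not rescue the sentence as written. It still conflicts with Section 9.1.2 on when the treatment period starts, still refers to a visit outside the schedule, and still calls pre-treatment events treatment-emergent. A SAP rule would help the tables, but the protocol text would remain contradictory.

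**Conclusion.** The concern holds as a defect of definition. Section 10.4 conflicts with Section 9.1.2 and with first application at Study Visit 1, its screening period has no identifiable end, and its use of treatment-emergent covers events before treatment.

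The consequence depends on a rule that the text does not give. Under assignment by onset date with screening ending at Study Visit 1, 7 of 42 treatment days (17% of planned exposure) fall in neither period. If Screening Visit 2 means Study Visit 2, the same week is reported as screening. Under assignment by recording visit nothing is lost, but some pre-treatment events may be counted as on treatment. These figures assume visits on their nominal days and the full 42 days of treatment.

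The effect is confined to how events are tabulated. Adverse event collection and the efficacy analyses are untouched. The point should be settled before database lock, while the choice cannot be influenced by where events happened to fall.

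**What to change.** In Section 10.4 and in the SAP:

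- Define a treatment-emergent adverse event as one with onset, or worsening, from the first application at Study Visit 1 through Study Visit 7/Exit.
- State that events are assigned to periods by onset date, not by the visit at which they are recorded.
- Report events with onset from consent to first application separately as pre-treatment, without the term treatment-emergent.
- Remove the reference to Screening Visit 2.

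The cost is one rewritten sentence and a before/after-application flag for events on the day of Study Visit 1. No visit or assessment is added. Section 12.4 already requires an onset date for each event entered in the eCRF. It does not list a date of worsening, so the eCRF instructions should say how a worsened pre-existing event is dated.
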